Subjects currently taking the following therapies are excluded: GLP-1 receptor agonists (e.g., Byetta®, Bydureon®, Adlyxin®, Victoza®, Saxenda®, Trulicity®, Tanzeum®, Ozempic®), Amylin analogs (e.g., Symlin®), Thiazolidinediones (e.g., Actos®, Avandia®) and any combination of these medications (e.g., Avandamet®, Avandaryl®, Duetact®, Actoplus Met®, PioMet®), Acarbose (Glucobay®), Miglitol (Glyset®). Additionally, subjects taking oral and injectable corticosteroids (e.g., prednisone), oral and injectable antibiotics, opioids and probiotics or other medications that alter gastrointestinal motility, chemotherapy, radiation, cytotoxic therapy, immune suppressants, antiepileptic drugs, colesevelam (Welchol®), and other supplements containing butyrate are also excluded from the study.			
Efficacy and Safety Evaluations			
Primary	Insulin sensitivity, as measured by the estimated glucose disposal rate (eGDR), a validated clinical tool for estimating insulin sensitivity in T1D		
Secondary	The following secondary evaluations will be performed: 1. Glucose variability 2. Triglycerides 3. Insulin usage, as reported on diary card		
Safety	Blood pressure, physical exam, chemistry, hematology and treatment-emergent adverse events		
Exploratory	1,5 AG and hs-CRP		

CLINICAL PROTOCOL SYNOPSIS		Protocol No.:	CL-301
Sponsor: Mayo Clinic		Investigator: [name]	
Statistical Analysis of Primary Endpoint:	Primary and Secondary Efficacy Data: The primary endpoint is the change from baseline (Day 0) to Day 48 in insulin sensitivity as measured by eGDR. The secondary endpoint of glucose variability (as measured from CGM data) is also the change from baseline (Day 0) to Day 24 and Day 48. However, the secondary endpoint of lowering of triglycerides measurements will be calculated from the baseline at Day -28.		
	Safety Data: Assessment of safety will be made using the change from baseline in vital signs, physical exam, chemistry, hematology, and treatment-emergent adverse events. The safety analysis set will include all Subjects that received any amount of study treatment. The safety analysis set will include all Subjects that received any amount of study treatment.		
	Sample Size Estimates: Sample size estimates are based on practical considerations.		
Synopsis Date: July 18, 2022, Amendment 2, Version 3.0			

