2. STUDY PURPOSE AND OBJECTIVES

This study will test the hypothesis that delivery of the butyrate-containing BKR-017 tablet to the colon of T1D subjects will improve insulin sensitivity. Additionally, the effect of BKR-017 on triglycerides and glucose variability will be assessed. The safety and tolerability of repeat dosing (up to 48 days of administration) of BKR-017 will be determined. By exploration of the effects of BKR-017 on various metabolic biomarkers, the data generated from this study will be used to support continued evaluations of BKR-017 as non-prescription product for T1D patients requiring

nutritional support to improve cardiometabolic health. Furthermore, these data will support continued evaluation of BKR-017 for the regulation of weight and hypertriglyceridemia.

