7.3.2 Secondary and Exploratory Efficacy Assessments

Secondary and exploratory evaluations will also be performed. The specific evaluations and sample collection and analysis time points are listed in [Table 3](#), [Appendix 2](#).

Secondary efficacy evaluations require measurement of glucose variability, insulin usage, and triglycerides. Study personnel will enter the results into the eCRF.

For the secondary endpoint of glucose variability, Dexcom CGM sensors will be supplied by BioKier and used to record continuous glucose levels every 5 minutes during the study.

The CGM sensor is water-resistant and **must** be applied to the subject's abdomen. The CGM sensor is held in place with a self-adhesive pad and requires no subject interaction with the device or the need for calibration.

The CGM continuously measures glucose in interstitial fluid through a small (5mm long, 0.4mm wide) filament that is inserted just under the skin. It records glucose levels every 5 minutes, capturing up to 2880 glucose results for up to 10 days. Subjects will be instructed to keep their Dexcom CLARITY app active, so that glucose monitoring data can be accessed by the study team throughout the study. When the subject returns to the OPC at Visit 2, the CGM sensor will be removed by study staff and the data stored on the sensor will be retrieved by the reader and downloaded to the Dexcom CLARITY data storage location. The data will then be accessed by Mayo personnel and authorized BioKier personnel, including the statistician.

The other secondary efficacy endpoint, triglycerides, will be measured in blood samples from Visits 1, and 2 by the Mayo Clinic Laboratory.

Exploratory evaluations require analysis of the laboratory tests for hsCRP and 1,5-AG, from samples obtained Visits 1 and 2.

All blood samples for exploratory evaluations will be collected and will be processed according to Mayo Clinic's established procedures. All analytical testing will be performed on the secondary

and exploratory endpoints by validated/established Mayo Clinic test methods or by methods routinely performed in the Mayo Clinic Core Laboratory.

Study personnel will enter the exploratory test results into the eCRF.

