11.1.3 Secondary Efficacy Endpoints

Secondary endpoints include:

1. Glucose variability (from CGM data)
2. Fasting triglycerides
3. Insulin usage (from diary card)

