12.6.2 Secondary Efficacy Analysis

Blood glucose variability will be calculated for each subject, for each 24-hour day (midnight to midnight) during which a CGM device recording is available for the entire 24-hour period. Results will be presented graphically for each subject by study day.

Triglyceride changes at Day -28 and Day 48 will be summarized as change from baseline where Day -28 is considered baseline.

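### Section 12.6.2 takes glucose variability no further than per-subject plots: no metric, paired change or interval, and the synopsis time points do not fit its complete-day rule

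*Combined protocol and SAP*

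**What the plan says.** Section 2 commits the study to an answer on this endpoint: "the effect of BKR-017 on triglycerides and glucose variability will be assessed". Section 11.1.3 lists glucose variability among three secondary endpoints.

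The synopsis, in its statistical analysis row, defines the endpoint as a change: "The secondary endpoint of glucose variability (as measured from CGM data) is also the change from baseline (Day 0) to Day 24 and Day 48". The synopsis design paragraph instead sets glucose variability after seven weeks of treatment against Day -28.

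Section 12.6.2 gives the analysis. It begins "Blood glucose variability will be calculated for each subject, for each 24-hour day (midnight to midnight", limits this to days with a full 24-hour recording, and ends with "Results will be presented graphically for each subject by study day". Nothing further is specified for this endpoint.

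The same section does give triglycerides a change: "Triglyceride changes at Day -28 and Day 48 will be summarized as change from baseline where Day -28 is considered baseline". Section 12.6.3 gives the two exploratory markers paired t-tests. Section 12.1 refers to a separate SAP for further detail; the document contains no such SAP.

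**The concern.** The endpoint is defined as a change, but the analysis section never computes one. Followed as written, 12.6.2 produces a set of individual graphs and no statement of how much variability changed on average or how uncertain that is.

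With no named metric, the choice between SD, CV or another measure stays open until the data are in hand. That choice matters: SD tends to fall when mean glucose falls, so a drop in SD need not mean lower relative variability. The study is open-label and single-arm, and Section 11 places the analysis under the direction of the manufacturer's personnel. Unstructured reading of individual plots is therefore exposed to selective interpretation.

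**Working it through.** **Step 1. Set the endpoint definition against the complete-day rule.**

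| Anchor | Where it appears | What the schedule does to it |
|---|---|---|
| Day -28 | Synopsis, design paragraph | Section 6.2.1 places the visit before midday and supplies the study sensors there, so the study sensor gives no complete Day -28. Subjects already use a Dexcom device, but use of earlier readings is not described. |
| Day 0 | Synopsis, statistical row | Section 6.2.2 has the first dose taken before the mid-day meal, so a complete Day 0 recording is part off and part on product. |
| Day 24 | Synopsis, statistical row only | Can be a complete day, but no other section mentions it. |
| Day 48 | Both synopsis paragraphs | Section 6.2.2 has the subject attend before noon and the sensor removed at that visit. Day 48 is complete on the study sensor only if the visit falls late in its window. |

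The synopsis is dated Amendment 2, Version 3.0, and the protocol Amendment 5, Version 6. The Day 0, 24 and 48 definition may therefore be a remnant.

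**Step 2. Which days are usable.** Nominally, complete days wholly before product are Days -27 to -1, which is 27 days. The required 96 doses at two per day cover 48 days, Days 0 to 47. The last 28 days before a Day 48 visit are Days 20 to 47 (47 - 28 + 1 = 20), all on product. Section 1 says the placebo effect on daily glucose in type 2 diabetes diminishes by about three weeks, so a window starting near there fits the protocol's own reasoning.

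**Step 3. Period means against single days.** Assume, for illustration, independent days with common within-subject variance s². A difference between two single days carries day-to-day variance 2s². A difference between means over 27 and 28 days carries (1/27 + 1/28)s² = (0.0370 + 0.0357)s² = 0.073s². Correlated or lost days shrink this gain, and averaging does not reduce true differences between subjects in their response. The direction is still clear.

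**Step 4. Precision of a paired mean change.** The plan gives no alpha, power, effect size or SD for this endpoint, so there is no figure to reproduce. Inputs for n:

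- 12 from Section 11.2
- 13 expected completers and 16 enrolled from Section 4.1
- about 11 if the synopsis's approximate 30% discontinuation applies to 16 (16 × 0.70 = 11.2)

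Formula: 95% half-width = t(0.975, n-1)/√n, in units of the SD of the within-subject change.

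- n = 11: 2.228/3.317 = 0.672
- n = 12: 2.201/3.464 = 0.635
- n = 13: 2.179/3.606 = 0.604
- n = 16: 2.131/4 = 0.533

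If a paired t-test is added, the change detectable with 80% power at two-sided 0.05 (both assumed) is 0.89 SD at n = 12 and 0.85 SD at n = 13, from the noncentral t distribution.

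**The case against.** The strongest reply is that a change is specified, in the synopsis, and that Section 12.1 sends further detail to a SAP. Both are true. A reader might infer that the trial will produce no estimate of change and that its result will rest on graphs alone. The documents do not support that: they show only that 12.6.2 specifies no estimate. The synopsis definition, however, is not carried into the analysis section, conflicts with the design paragraph, and uses days that fit the complete-day rule poorly. A SAP would still have to resolve this.

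A second reply is that descriptive reporting is acceptable in a small single-arm, open-label study meant for preliminary conclusions. That stands against demanding a test. Triglycerides also get none, and no ranking of endpoints is stated, so being listed first carries little weight. But a descriptive analysis still needs a defined quantity and an estimate.

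Two further inferences go too far. Section 7.3.2 says of the CGM data downloaded at Visit 2: "The data will then be accessed by Mayo personnel and authorized BioKier personnel, including the statistician". A reader might conclude that the manufacturer's statistician sees them before database lock; neither 7.3.2 nor 10.2 orders access against lock. A reader might also attach a false-positive rate to counting plots that look improved; the plan contains no counting rule, so it has no such rate.

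**Conclusion.** The point holds as a gap between endpoint and analysis. In this document, glucose variability has no named metric, averaging window, within-subject change, group estimate or interval, and the synopsis gives two baselines that do not agree. It should be corrected, but it does not touch the primary endpoint.

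The size can be given only in standardised form: a paired mean change would be known to about ±0.64 SD of change at n = 12 and ±0.60 at n = 13, ranging from 0.67 (n = 11) to 0.53 (n = 16). This assumes roughly normal changes and that n counts subjects with usable data in both windows, since Section 12.2 imputes nothing. With no SD in the document, any range in CV points would be unsupported.

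The conclusion is limited by the absent SAP, which may already contain a remedy. A neighbouring gap should be closed at the same time: insulin usage, also a secondary endpoint, has no analysis in 12.6.2 at all.

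**What to change.** Amend 12.6.2, and the SAP to match:

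- Name the metric, for example daily CV (SD divided by mean) per complete day. State how many of the 288 five-minute readings (2880 over 10 days) a day needs to count as complete.
- Average it per subject over complete run-in days before Day 0, and over complete days in a stated late on-product window, for example the last four weeks before Visit 2. Set a minimum number of valid days for each window.
- Report the mean paired change with its 95% confidence interval. A paired t-test is optional. Keep the per-subject plots as supportive displays.
- Amend the synopsis design paragraph and statistical row to the same windows. Either define Day 24 as a window of its own, noting that it would fall inside a Day 20 to 47 window, or drop it explicitly.
- Finalise the text before on-treatment CGM data are examined for efficacy. Routine compliance and safety review need not wait.

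The cost is protocol and SAP wording and one extra table, using data already being collected. The small downside for the sponsor is that a null result becomes visible.

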12.6.3 Exploratory Efficacy Analysis

1,5 AG values at Day 48 will be compared to baseline (Day -28) with paired t-tests.

hs-CRP values at Day 48 will be compared to baseline (Day -28) with paired t-tests.

12.7 Safety Analysis

12.7.1 Adverse Events

The number and percentage of subjects experiencing adverse events reported during the test product administration period will be summarized by body system and preferred term for all subjects in the safety analysis set. Statistical testing will not be performed.

12.7.2 Laboratory Data

Selected laboratory tests will be summarized using an eight-number summary (sample size, mean, median, standard deviation, 25th quartile, 75th quartile, minimum, and maximum values) by visit. In addition, reported, graded laboratory abnormalities will be summarized for each laboratory test. Statistical testing will not be performed.

12.7.3 Vital Signs

Vital signs will be summarized by visit using an eight-number summary (sample size, mean, median, standard deviation, 25th quartile, 75th quartile, minimum, and maximum values). Statistical testing will not be performed.

13. ETHICAL CONSIDERATIONS

13.1 Regulatory and Ethical Compliance

This clinical study was designed and will be implemented in accordance with the ethical principles established in the Declaration of Helsinki.

13.2 Informed Consent Procedures

Eligible subjects may only be included in the study after providing written (witnessed, if required) consent using an Institutional Review Board (IRB)-approved ICF. Informed consent must be obtained before conducting any study-specific procedures. The process of obtaining informed consent should be documented in the subject's medical record. Information should be given in both oral and written form and subjects must be given ample opportunity to inquire about details of the study.

13.3 Responsibilities of the Investigator and IRB

The protocol and the proposed informed consent form must be reviewed and approved by a properly constituted IRB before subjects can be enrolled in the study. For this study, Mayo Clinic IRB will be responsible for protecting the rights and welfare of human research subjects involved in the research activities and Mayo Clinic policies and procedures will be followed.

A signed and dated statement that the protocol and informed consent have been approved by the IRB must be provided to BioKier before study initiation. Prior to study start, the investigator is required to sign a protocol signature page confirming agreement to conduct the study in accordance with the protocol and to give access to all relevant data and records to BioKier representatives including study monitors, and Mayo Clinic IRB, as required.

13.4 Publication of Study Protocol and Results

Upon study completion and finalization of a study report, the results of this trial may be submitted for publication in accordance with the publication terms defined in the Clinical Study Agreement.

13.5 Protocol Adherence

Deviations from the protocol should be avoided. All protocol deviations will be documented, recorded in the eCRF, and reported in the study report. Deviations will be reported to the Clinic IRB in accordance with their requirements. No waivers will be granted by the study sponsor.

13.6 Protocol Amendments

Any change or addition to the protocol can only be made in a written protocol amendment that must be approved the Mayo Clinic IRB. Only amendments that are required for subject safety may be implemented prior to Mayo Clinic IRB approval. Notwithstanding the need for approval of formal protocol amendments, the investigator is expected to take any immediate action required for the safety of any subject included in this study, even if this action represents a deviation from the protocol. In such cases, the Mayo Clinic IRB will be informed in conformance with the IRB requirements.

14. APPENDICES

14.1 APPENDIX 1: Previous Human Experience with Butyrate

Table 2: Previous human experience with butyrate (selected studies)

Patient Type	Stage	Dose/ Administration	Route of	Duration	Reference
Oral and Colon-Targeted Formulations Type 2 Diabetes					
Type 2 diabetes	Efficacy, safety	1g/ rectal infusion		Single dose	BioKier Study ⁸
Type 2 diabetes	Efficacy, safety	3g/day butyrate suppositories		4 weeks	BioKier Study (data on file)
Type 2 diabetes	Efficacy	6 x 100mg sodium butyrate capsules, orally		45 days	^{35;36}
Oral and Colon-Targeted Formulations in Other Patient Populations					
Cancer, advanced solid tumors	Phase 1	50-400 mg/kg/d, oral		2 x 3 weeks	³⁷
Cancer, advanced solid tumors	Pilot efficacy, safety	150-200 mg/kg TID, oral			²⁹
Crohn's disease	Pilot efficacy, safety	4g/d, oral – enteric-coated tablets		8 weeks	²⁸
Chronic pouchitis	Pilot efficacy, safety	4.4g/d, suppository		3 w	²⁷

14.2 APPENDIX 2: Tables

Table 3: Safety Hematology Laboratory Tests

		Screening	Test Period
	Visit	1	2
	Day	- 28	48
White Blood Cell Count (WBC)		X	X
Red Blood Cell Count (RBC)		X	X
Platelet		X	X
Hemoglobin		X	X
Hematocrit		X	X
Mean Corpuscular Volume (MCV)		X	X
Mean Corpuscular Hemoglobin (MCH)		X	X
Mean Corpuscular Hemoglobin Concentration (MCHC)		X	X

Table 4: Safety and Efficacy Chemistry Laboratory Tests

ASSESSMENTS	Visit	Screening	Test Period					
		1						2
	Day	-28						48
Blood Urea Nitrogen (BUN)		X						X
Creatinine		X						X
Sodium, Calcium, Chloride, and Potassium		X						X
Carbon Dioxide		X						X
Total Protein		X						X
Albumin		X						X
Bilirubin (total)		X						X
Aspartate Aminotransferase (AST)		X						X
Alanine Aminotransferase (ALT)		X						X
Alkaline Phosphatase (ALP)		X						X
Cholesterol		X						X
Triglycerides		X						X
HDL		X						X
LDL		X						X
Glucose		X						X
CRP		X						X
HbA1C		X						X
Urine pregnancy test		X						X
Exploratory								
High-sensitivity C-reactive protein (hsCRP)		X						X
1,5-Anhydroglucitol (1,5-AG)		X						X

